We computed the power of a one-sided Wilcoxon signed-rank to detect a significant difference between the frequencies of CD4 binding-site, or V2 apex or V3 glycan epitope (bnAb site at the base of the V3 loop), or CH505TF-specific IgG+ B cells observed at baseline with that observed at one time point post-vaccination. The power was evaluated as a function of (1) the effect size, defined here as the average change (increase) in the frequencies of (eg) CD4 binding-site or V3 glycan (base of the V3 loop) binding-IgG+ B cells after vaccination relative to baseline, and (2) the standard deviation (SD) of the difference between pre- and post-vaccination frequencies. The calculations made the following assumptions:

- The average increase in the frequency of CD4 binding-site IgG+ B cells post-vaccination relative to baseline in study participants ranges between 0 and 5%.
- The standard deviation of the frequency of CD4 binding-site IgG+ B cells post-vaccination relative to baseline in study participants ranges between 0.5% and 4%.
- The increase in the frequency of CD4 binding-site IgG+ B cells after vaccination relative to baseline is normally distributed. Departure from this assumption is not expected to impact the power of the study because the Wilcoxon signed-rank test is nonparametric.

The calculations considered samples of size  $n = 12$  and  $n = 10$  to assess power when the data set is complete ( $n = 12$ ) and when 2 out of the 12 participants (or, equivalently, an attrition rate of approximately 17%;  $n = 10$ ) are lost to follow up before the post-vaccination time point.

The power function of the test under these different scenarios is presented in [Figure 6-1](#). For example, if the standard deviation of the change in the frequency of binding IgG+ B cells is  $SD = 2\%$ , the calculation indicates that a sample of size  $n = 10$  achieves almost 80% power to detect a significant increase at the 5% significance level if the average increase in the proportion of binding IgG+ B cells is 1.5%. With a sample of size  $n = 12$  (no loss to follow-up), the test has more than 80% power to detect a significant difference under the same scenario.

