## 6.2 Statistical analyses

This section describes the final study analysis, unblinded as to treatment arm assignment. All data from enrolled participants will be analyzed regardless of how many vaccinations they received. All analyses will be performed using SAS and R.

No formal multiple-comparison adjustments will be employed for multiple safety endpoints, multiple primary immunogenicity endpoints, or secondary endpoints. Statistical tests for comparisons of primary and secondary endpoints, including two- and one-sided tests, will use a significance level (alpha) of 5%.

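### The worked power example for the primary B-cell test does not follow from its own inputs (about 66% and 76% by the exact test, not almost 80% and more than 80%), and power is wrongly said not to depend on the distribution

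*Protocol*

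**What the plan says.** Protocol section 6.1.1 sets out the calculation for Group 1: "We computed the power of a one-sided Wilcoxon signed-rank to detect a significant difference" between baseline and one post-vaccination time point. The change is assumed to be normally distributed. Sample sizes are 12 (complete data) and 10 (two of 12 lost, about 17%).

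The worked example takes 2% as its standard deviation, "if the standard deviation of the change in the frequency of binding IgG+ B cells is" that value. It states that n = 10 "achieves almost 80% power to detect a significant increase at the 5% significance level if the average increase in the proportion" of binding cells is 1.5%. For n = 12 it states that "the test has more than 80% power to detect a significant difference under the same scenario". The level agrees with section 6.2, where all tests, "including two- and one-sided tests, will use a significance level (alpha) of 5" percent.

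On the normality assumption, section 6.1.1 adds: "Departure from this assumption is not expected to impact the power of the study because the Wilcoxon signed-rank test is nonparametric". Section 6.1.2 repeats this sentence for Part B. For single-group power in Groups 2, 3 and 4 it refers back to section 6.1.1 and Figure 6-1. The SAP gives only safety sample-size calculations, so it neither repeats nor corrects these figures.

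**The concern.** A mean increase of 1.5% with a standard deviation of the change of 2% is a standardized effect of 0.75. With 10 or 12 pairs, 80% power at that effect looks too high for any one-sided 5% test that has to estimate the spread from the data.

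The robustness sentence mixes up two properties. A rank test controls type I error without normality, provided the differences are symmetric about zero under the null. Its power still depends on the shape of the differences under the alternative.

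This is the only numerical power statement in the text for a primary immunogenicity endpoint, and all four groups rely on it. At n = 10 the type II error for this effect is about 34% with the exact test (about 30% with the uncorrected approximation), where the text implies about 20%.

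**Working it through.** **Inputs (Protocol 6.1.1; level confirmed in 6.2).** One-sided signed-rank test, level 5%; change normal with mean 1.5 and standard deviation 2 percentage points; n = 10 and n = 12. Standardized effect = 1.5 / 2 = 0.75.

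**Trying to reproduce the plan's figures.** The only formulas tried that exceed 80% at n = 12 treat the variance as known. Power = Φ(0.75√n − 1.645):
- n = 10: Φ(2.372 − 1.645) = Φ(0.727) = 76.6%
- n = 12: Φ(2.598 − 1.645) = Φ(0.953) = 83.0%

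Multiplying n by the signed-rank efficiency 3/π gives 74.9% and 81.4%. These fit the plan's wording loosely and may be its source, but that is an inference. Neither is the signed-rank test at these sample sizes.

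**The stated test.** W is the sum of the ranks of the positive differences. Under the null each rank enters with probability 1/2.
- Exact test: reject at W ≥ 45 for n = 10 (attained size 4.2%) and at W ≥ 61 for n = 12 (4.6%).
- Uncorrected normal approximation: reject when W > n(n+1)/4 + 1.645√[n(n+1)(2n+1)/24]. For n = 10 this is 27.5 + 1.645 × 9.81 = 43.6, so W ≥ 44 (true size 5.3%). For n = 12 it is 39 + 1.645 × 12.75 = 59.97, so W ≥ 60 (true size 5.5%).
- With a continuity correction the cut-offs are the same as for the exact test.

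Simulated power under the normal model (400,000 trials per n; simulation error below 0.1 point), with the paired t-test from the noncentral t distribution (noncentrality 0.75√n):

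| Version, one-sided 5% | n = 10 | n = 12 |
|---|---|---|
| Exact signed-rank | 65.6% | 75.6% |
| Normal approximation, corrected | 65.6% | 75.6% |
| Randomized to exactly 5% | 69.1% | 76.9% |
| Normal approximation, uncorrected | 70.2% | 78.6% |
| Paired t-test, for comparison | 70.7% | 78.5% |
| Protocol text | almost 80% | more than 80% |

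**What would give 80% with the exact test, standard deviation 2%.** A mean increase of about 1.8% at n = 10 (79.3%) or 1.6% at n = 12 (80.2%). At a mean increase of 1.5%, 13 pairs give 79.2% and 14 give 81.5%. Alternatively, a standard deviation of about 1.65% gives 80% and 88%, but the text applies its 2% to the change itself.

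**Dependence on shape.** Mean 1.5 and standard deviation 2 are held fixed, exact test. In the responder rows non-responders have mean 0, responders have mean 1.5/p, and both have normal spread s with s² = 4 − p(1 − p)(1.5/p)². For p = 0.4, s² = 4 − 0.24 × 14.06 = 0.625.

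| Shape of the change | n = 10 | n = 12 |
|---|---|---|
| 40% responders | 53% | 63% |
| Uniform | 60% | 70% |
| 50% responders | 62% | 73% |
| 60% responders | 64% | 75% |
| 75% responders | 65% | 75% |
| Normal | 66% | 76% |
| Laplace | 73% | 82% |
| Right-skewed exponential | 83% | 90% |

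**The case against.** Several points can be said for the plan, and most of them limit the finding.

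- **Test version.** The protocol does not say exact or asymptotic. This stands, so a range is needed. With the uncorrected approximation the n = 12 statement misses by less than 2 points. It is still not above 80%, and that version slightly exceeds the 5% level.
- **It is only an example.** The sentence illustrates a grid of effects from 0 to 5% and standard deviations from 0.5% to 4%. No sample-size target or decision rule rests on it. Part A could be topped up to 18 so that at least 12 contribute. Part B within-group tests are optional, and pooling two groups is offered. For the same effect and exact test, n = 20 gives 93% and n = 24 gives 96%. This stands: the error is in a stated figure, not in the design.
- **Partial response.** A reader might infer that power collapses whenever only some participants respond. The calculations do not support that. With this mean and standard deviation, a mixture with unresponsive non-responders is possible only if 2.25(1 − p)/p ≤ 4, that is p ≥ 36%, so 40% lies near the edge. From 60% upward the result is close to the normal one. A mixture with 25% at mean 4.5 and 75% at mean 0.5, each with standard deviation 1, gives 68.5% and 78.5%, above normal.
- **Figures.** Figures 6-1 and 6-2 were not available. Nothing shows that either is wrong, and the example may be a misread curve.

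**Conclusion.** The worked example is wrong on its own inputs. At a mean increase of 1.5% and a standard deviation of the change of 2%, power is about 66% (n = 10) and 76% (n = 12) with the exact test, or about 70% and 79% with the uncorrected approximation. The n = 12 statement fails under every signed-rank version tried; the n = 10 statement is too high by roughly 10 to 14 points. This rests on the protocol's normal model, one-sided 5% level and independent participants.

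The robustness sentence in sections 6.1.1 and 6.1.2 is also incorrect. Being nonparametric does not protect power, and departures from normality can lower or raise it.

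Two stronger readings are tempting. One is that the trial is too small; the documents set no power target that would show this. The other is that a null result will be taken as lack of activity. That is conjecture: the protocol also relies on response rates with confidence intervals and on tier 2 neutralization as a separate primary endpoint.

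**What to change.** - **Section 6.1.1, example.** Name the version of the signed-rank test. For the exact test, state about 66% power at n = 10 and 76% at n = 12 for a mean increase of 1.5% and a standard deviation of the change of 2%. Add that 80% power needs a mean increase of about 1.8% (n = 10) or 1.6% (n = 12) at that standard deviation.
- **Sections 6.1.1 and 6.1.2, robustness sentence.** Replace it with a statement that power depends on the shape of the differences and can move in either direction.
- **Figures.** Check Figure 6-1 against the named test, and Figure 6-2 as well if it came from the same code. Regenerate only if they do not match.

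The sample size, the test, its level and the analysis do not change. The cost is a few sentences, a check of the power code and less favourable stated figures.

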### 6.1.2 Power calculations for immunogenicity for Part B

The goal of Part B is to evaluate whether the three vaccine regimens tested in Groups 2, 3, and 4 elicit CD4 binding-site, V2 apex and V3 glycan epitope (bnAb region at the base of the V3 loop), and CH505TF-specific memory B cells. The primary endpoint will be the frequencies of CD4 binding-site, V2 apex and V3 glycan epitope (bnAb region at the base of the V3 loop), and CH505TF-specific IgG+ B cells at baseline and after vaccination, as measured by flow cytometry. Part B will also evaluate whether the vaccine regimens elicit autologous tier 2 virus neutralizing antibodies using the TZM-bl assay.

The statistical analysis will first compare the frequencies of CD4 binding-site, V2 apex and V3 glycan epitope, and CH505TF-specific IgG+ B cells at baseline with those observed after vaccination. These comparisons may be performed within each treatment group (ie, Group 2, 3, and 4) using Wilcoxon signed-rank tests. Should the vaccine regimens elicit a desired immune response, we expect the

frequencies of CD4 binding-site or V2 apex or V3 glycan epitope or CH505TF-specific IgG+ B cells to increase after vaccinations, and the tests will be one-sided. Additional analyses will compare the frequencies of CD4 binding-site, V2 apex and V3 glycan epitope, and CH505TF-specific IgG+ B cells at other time points following vaccination; these tests will be two-sided because the direction of the effect may not be known.

The statistical analysis will also perform response positivity calls for each study participant by comparing B cells frequencies at baseline to B cells frequencies post-vaccination using Fisher's exact tests. The statistical analysis will next assess whether the frequencies of CD4 binding-site, V2 apex and V3 glycan epitope, and CH505TF-specific IgG+ B cells differ between time points post-vaccination. These comparisons will be performed using two-sided Fisher's exact tests. We will next estimate the response rate at each post-vaccination time point within each group by the empirical proportion of positive calls among study participants. Associated 95% confidence intervals will also be built.

[figure not shown]
We evaluated the power of a one-sided Wilcoxon signed-rank to detect a significant difference between the frequencies of CD4 binding-site, or V2 apex or V3 glycan epitope (bnAb site at the base of the V3 loop), or CH505TF-specific IgG+ B cells observed at baseline with that observed at one time point post-vaccination in one of the treatment group (ie, either Group 2, 3, or 4; see Section 6.1.1) and when two groups are combined (eg, Groups 2 and 4; see results below). The power was evaluated as a function of (1) the effect size, defined here as the average change (increase) in the frequencies of (eg) CD4 binding-site or V3 glycan (base of the V3 loop) binding-IgG+ B cells after vaccination relative to baseline, and (2) the standard deviation (SD) of the difference between pre- and post-vaccination frequencies. The calculations made the following assumptions:

- The average increase in the frequency of CD4 binding-site IgG+ B cells post-vaccination relative to baseline in study participants ranges between 0 and 5%.
- The standard deviation of the frequency of CD4 binding-site IgG+ B cells post-vaccination relative to baseline in study participants ranges between 0.5% and 4%.
- The increase in the frequency of CD4 binding-site IgG+ B cells after vaccination relative to baseline is normally distributed. Departure from this assumption is not expected to impact the power of the study because the Wilcoxon signed-rank test is nonparametric.

The calculations considered samples of size  $n = 12$  and  $n = 10$  to assess power when the data set is complete ( $n = 12$ ) and when 2 out of the 12 participants (or, equivalently, an attrition rate of approximately 17%;  $n = 10$ ) are lost to follow up before the post-vaccination time point. The power function of the test under these different scenarios when carried with each group separately (i.e., within either

Group 2, or 3, or 4) is discussed in Section 6.1.1 in the context of Group 1 (Part A); see also Figure 6-1.

The effect of vaccination with Alum as well as that of the dose of 3M-052-AF on immune responses may be performed using nonparametric one-way analysis of variance (ANOVA) (eg, Wilcoxon rank sum tests). To increase the power of statistical tests, these comparisons may be carried out by combining all four groups together and using nonparametric two-way ANOVA (eg, Friedman-type or Skillings-Mack tests) that include vaccination with Alum and vaccination with 3M-052-AF as factors.

Since participants will not be randomized between Groups 1, 2, 3, and 4 at enrollment, comparisons of immunogenicity endpoints between treatment groups will be cautiously interpreted. Differences in baseline characteristics may be examined to determine whether differences between groups could have been induced by (eg) differences in the demographics of study participants between treatment groups.

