## 6 Statistical considerations

### 6.1 Sample size justification and accrual

Recruitment will target enrolling a total of 48 healthy, HIV-uninfected adult participants in 4 groups.

In Part A, recruitment will target enrolling 12 healthy, HIV-uninfected adult participants in Group 1. The protocol team will convene after the 12th participant has received their third vaccination to determine if further participants should be enrolled to evaluate immunogenicity. Examples of reasons that might necessitate enrollment of additional participants are provided in Section 1.5. If some participants from the original number of 12 enrolled will not contribute data to some of the immunogenicity analyses, the protocol team may enroll additional fully evaluable participants, up to 6 additional participants, or a total of 18 participants enrolled, with the goal of at least 12 contributing to the final immunogenicity analyses.

In Part B, recruitment will target enrolling a total of 36 healthy, HIV-uninfected adult participants in Groups 2, 3, and 4 ( $n = 12$  participants per group). Enrollment in Groups 2, 3, and 4 will be stepwise by group, starting with Group 2, continuing with Group 3, and finishing with Group 4.

Every study participant will be followed for an AESI contact 12 months after the last vaccination received (for example, following participants until Month 16 if they receive 3 vaccinations, or Month 24 if they receive 5 vaccinations).

Detail about the pace of enrollment can be found in Section 1.5.

Since enrollment is concurrent with receiving the first vaccination, all participants will provide some safety data. However, for immunogenicity analyses, data may be missing for a variety of reasons, including participants terminating from the study early, problems in shipping specimens, or high assay background. Immunogenicity data from 17 Phase 1 and 2 Phase 2a HVTN vaccine trials, which began enrolling after June 2005 (data as of September 2014), indicate that 17% is a reasonable estimate for the rate of missing data.

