### 6.2.2 Immunogenicity analyses

The frequencies of CD4 binding-site, V2 apex and V3 glycan epitope (bnAb region at the base of the V3 loop), and CH505TF-specific IgG+ B cells elicited by the vaccine measured by flow cytometry, the response rate and magnitude of binding measured by the BAMA assay, and the area-under-the-magnitude-breadth curve (AUC) (27) to panels of viral isolates measured by the HIV-1 neutralization TZM-bl assay, will be summarized using descriptive statistics. Data will be tabulated and graphically displayed by visit number and by number of doses received.

Discrete categorical assay endpoints (eg, response rates) will be analyzed by tabulating the frequency of positive response. Crude response rates will be presented with their corresponding 95% confidence interval estimated based on the score test method (26). The Barnard's exact tests may be employed to compare the response rates of certain immune responses between the test vaccine and other candidates in the CH505 family.

Quantitative assay endpoints (eg, frequencies of memory B-cells) will be summarized by time point. Nonparametric paired comparisons will be performed using Wilcoxon signed-rank tests, and the Wilcoxon rank sum test will be used to compare independent samples. More details of the analyses of each assay will be provided in the statistical analyses plan (SAP).

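### The optional pooled Alum-by-dose analysis names Friedman-type and Skillings-Mack tests, which as standardly defined do not fit four independent groups; a stratified rank test would deliver the power gain sought

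*Protocol*

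**What the plan says.** Protocol section 6.1.2 lists four between-group comparisons: two for Alum (Group 2 v 3, Group 1 v 4) and two for 3M-052-AF dose (Group 1 v 3, Group 2 v 4). Each may be done with Wilcoxon rank-sum tests. It then adds: "To increase the power of statistical tests, these comparisons may be carried out by combining all four groups together", using "nonparametric two-way ANOVA (eg, Friedman-type or Skillings-Mack tests) that include vaccination with Alum and vaccination with 3M-052-AF as factors". No power, effect size or block definition is given for this pooled analysis.

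The design facts that bear on it are:

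- **Separate people in each group.** Protocol section 6.1: "recruitment will target enrolling 12 healthy, HIV-uninfected adult participants in Group 1", and "recruitment will target enrolling a total of 36 healthy, HIV-uninfected adult participants in Groups 2, 3, and 4", 12 per group.
- **No randomisation and no matching.** Section 6.1.2 begins its caution about group comparisons with "Since participants will not be randomized between Groups 1, 2, 3, and 4 at enrollment". Neither document defines a matched set or a participant-level block across groups.
- **Independent samples are recognised as such.** Section 6.2.2: "the Wilcoxon rank sum test will be used to compare independent samples".
- **Detail is deferred.** Section 6.2.2 leaves assay-level detail to the SAP. The SAP supplied covers safety and tolerability only (sections 2 and 4) and does not specify this test.

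**The concern.** The Friedman test ranks treatments within a block that contains one observation per treatment, as in repeated-measures or matched data. Skillings-Mack extends it to blocks with missing observations, not to several observations per cell. Here each participant sits in exactly one Alum-by-dose cell, and each cell holds about 12 unrelated people. Both named examples therefore need a structure that the trial does not have.

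Two smaller mismatches follow from the same sentence. Every group receives 3M-052-AF, so vaccination with it has a single level; the factor that varies is its dose. In addition, these tests treat one factor as a nuisance block, so they do not test whether the dose effect differs with and without Alum.

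What is at stake is the power of the Alum and dose comparisons. Protocol section 2.5 gives the dose comparison as the reason for the 3 mcg arms. With 12 v 12 the separate comparisons are weak, so a valid pooled test is worth having. Leaving an unsuitable test in the plan means the real choice is made after the data are seen.

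**Working it through.** The plan states no figure for the pooled analysis, so there is none to reproduce. The check asks what the named tests do under each literal reading, and what a suitable test would do.

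**Inputs.** From the documents: four groups of 12, 5% level, and 10 per group after the 17% missing-data rate (Protocol sections 6.1, 6.1.2, 6.2). Assumed: two-sided tests, normal responses with equal SD, and shifts of 0.8 and 1.0 SD between dose levels.

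**1. One summary value per cell, other factor as block.** This gives b = 2 blocks and k = 2 treatments. The Friedman statistic is Q = 12/[bk(k+1)] × ΣR² − 3b(k+1). The most extreme rank sums are 2 and 4, so

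Q = 12/(2×2×3) × (4 + 16) − 3×2×3 = 20 − 18 = 2.0.

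The 5% critical value on 1 df is 3.84. At Q = 2.0 the chi-square p is 0.157 and the exact two-sided p is 2 × (1/2)² = 0.5. Power is zero at any effect size.

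**2. Unrelated participants lined up as blocks.**

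- *Four-group Friedman.* Re-ordering the rows of a simulated 4 × 12 data set (0.8 SD shift) 2,000 times moved the central 95% of p-values over 0.013 to 0.46 in one data set and 0.004 to 0.23 in another. Not every data set straddles 5%, but nothing in the plan fixes the order.
- *The same test does not isolate dose.* With no dose effect and an Alum shift of 1 SD, it rejects about 65% of the time.
- *Two-treatment Friedman on 24 arbitrary pairs.* At 1.5 points with SD 2 (0.75 SD), power is 58%, with size about 6% to 7%. That exceeds a single 12 v 12 test (39%), but the answer depends on the pairing and the size is above 5%.

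**3. A rank test for independent replicated cells.** Rank within each Alum stratum and add the two rank sums for the higher-dose arm. Per stratum, with n per arm, the null mean is n(2n+1)/2 and the null variance is n²(2n+1)/12. For n = 12 these are 150 and 300, so

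z = (W₁ + W₂ − 300)/√600, with √600 = 24.49.

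This is van Elteren, and equals Mack-Skillings at equal cell sizes.

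Hand approximation at 0.8 SD: P(X > Y) = Φ(0.8/√2) = 0.714, and the expected excess per stratum is 144 × 0.214 = 30.8.

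- Pooled: 61.7/24.49 = 2.52, so power ≈ Φ(2.52 − 1.96) = 71%.
- Single test: 30.8/17.32 = 1.78, so power ≈ Φ(1.78 − 1.96) = 43%.

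Simulation, which does not rely on the null variance, gives:

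| Per cell | Shift | Pooled stratified test | One exact rank-sum test |
|---|---|---|---|
| 12 | 0.8 SD | about 73% | about 43% |
| 12 | 1.0 SD | about 90% | about 61% |
| 10 | 0.8 SD | about 66% | about 36% |
| 10 | 1.0 SD | about 84% | about 51% |

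The size of the pooled test is about 5%. At 1.5 points with SD 2 and 12 per cell, power is 68% pooled against 39% for the single test.

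**The case against.** The best case for the plan has four parts.

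- **The text is permissive.** It says "these comparisons may be carried out by combining all four groups together", offers the tests only as examples, and gives no power figure. The rank-sum tests named alongside are valid, and group comparisons are to be read cautiously. This stands. The pooled analysis is optional, and Part B's main question is answered within groups.
- **Friedman-type can be read broadly.** A replicated form, with the other factor's level as the block, is Mack-Skillings. It is valid here, and its name is easily confused with Skillings-Mack. The documents cannot show what was meant. This stands as a possibility, but Skillings-Mack as written is a different test, and no block is defined that would point to the replicated form.
- **Nobody proposed cell summaries or arbitrary rows.** True. They are simply the literal ways of giving these tests the one-per-cell data they need.
- **An immunogenicity analysis plan may exist elsewhere.** It may. In the documents supplied, section 6.1.2 is the only specification.

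The factor label is a matter of wording: the preceding sentence in section 6.1.2 does speak of dose.

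**Conclusion.** Wrong as written, and should be changed. As standardly defined, the two named tests do not suit four independent, unmatched groups. Used literally, they either cannot reach 5% or give a p-value that depends on an arbitrary pairing, so they do not deliver the power gain sought in any dependable form.

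Two stronger conclusions might be inferred, and the documents support neither. The first is that pooling brings no gain. It does: about 30 percentage points at either assumed shift with 12 per cell (73% v 43%, 90% v 61%), provided the test is valid. The second is that no Friedman-type method can analyse these groups. The replicated-block form can.

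The power figures rest on assumed shifts, normal responses, two-sided testing and effects that are equal in both strata. The documents state no between-group effect or SD. The mismatch between test and design depends on none of these.

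**What to change.** In Protocol section 6.1.2, and in whatever plan governs the immunogenicity analysis:

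1. Replace the two examples with van Elteren (stratified Wilcoxon) or the equivalent Mack-Skillings test, with the Alum effect stratified by 3M-052-AF dose level and the dose effect stratified by Alum. State the stratum weights for unequal cell sizes.
2. Call the second factor dose of 3M-052-AF.
3. State that the stratified test assumes effects in the same direction in both strata. Check the interaction separately with an aligned-rank model or a linear model on the log scale.
4. Reconcile the factor levels. Section 6.1.2 describes 3 mcg and 500 mcg for Group 3, while the footnote to the schema table in SAP section 3.5 reports that participants received 2.2 mcg of 3M-052-AF and 556 mcg of Alum. The comparisons that use Group 3, and its stratum, need a definition that agrees with both documents.
5. Give the power of the pooled test with its assumed effect.

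The cost is a few sentences. No further data are needed, and the methods are standard in SAS and R, which the protocol already names.
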